# 5.2.3 Colonoscopy (Visit 2, Day 2)

Colonoscopy will be performed on the morning following completion of the preparation.

Subject's vital signs and weight will be measured. A blood sample will be collected during anaesthesia for sulphate assessment testing by central lab and for biochemistry testing by local lab. A urine sample will be collected prior to anaesthesia for sulphate measurement by central lab and another one for urinary analysis by local lab.

The colonoscopy will be performed by a physician according to the site's standard procedures. Cleanliness will be evaluated on a 4-point scale, as shown in Section 7.3.1 as well as using the BBPS (See Section 7.3.2.1). Additional data will be collected as outlined in Section 7.2.

The subject will be discharged from the hospital after the colonoscopy (unless there is a medical reason/condition for retaining the subject).

The following procedures will be performed on day of colonoscopy (Day 2):

- Review and recording of AEs
- Body weight
- Vital signs (temperature, supine BP and HR)
- Blood and urine sample for local lab
- Blood and urine sample for central lab sulphate testing
- Colonoscopy
- Colonoscopy-related assessments, including suspected diagnosis
- Histological examination of colonic biopsy (if needed)
- Drug accountability by unblinded site personal
- Reporting of study administration compliance data (based on subject's leaflet information) by unblinded site personal
- Subject status at the end of the visit

# 5.2.4 Procedures after Study Treatment

# 5.2.4.1 Phone Contact (Visit 3)

The investigator will contact the subject by phone on Day  $4\pm1$  to collect data on potential AEs.

**PAGE 43/103** 

# 5.2.4.2 End of Study Visit (Visit 4) or Early Withdrawal Visit

Subjects will return to the study centre 30 days (-5+/15 days) after colonoscopy. A physical examination will be performed, vital signs measured and the subject will be queried for occurrence of AEs and changes in concomitant medications. If any laboratory result is considered clinically significant by the investigator (and documented as an AE), a follow-up sample should be collected and sent for analysis. The subject will be followed-up until resolution of the AE.

For subjects who complete the study, or for those who withdraw prematurely from the study, final evaluations will be performed as soon as possible afterwards. Subjects with ongoing AEs or clinically significant laboratory test abnormalities (as determined by the investigator) will be monitored as described in Section 8.1.3 and Section 8.1.2.4, respectively.

The following procedures will be performed at the End of Study (Visit 4, Day 32 (-5/+15 days i.e. Day 27 to Day 47), or Early Withdrawal visit:

- Review of AEs
- New or changed concomitant medications
- Concomitant non-drug therapies
- Concomitant surgical procedures
- Physical examination
- Vital signs (temperature, BP and HR)
- Body weight
- Collection of blood and urine samples for blood sulphate measurement by central lab
- Collection of blood for biochemistry analysis and urine for local laboratory analysis
- Subject status at the end of the visit.

PAGE 44/103

#### 6 TREATMENT OF SUBJECTS

# 6.1 Study Drugs Administered

Following confirmation of eligibility for the study, subjects will be allocated to one of the following treatment groups:

• Eziclen®/Izinova® concentrate sulphate salt solution

or

• Klean-Prep®, powder for oral solution dosage

#### 6.1.1 Eziclen®/Izinova®

The bowel cleansing preparation Eziclen®/Izinova® is a concentrate for oral solution packaged in two bottles, each of them contains: sodium sulphate anhydrous: 17.510 g, magnesium sulphate heptahydrate: 3.276 g, potassium sulphate : 3.130 g, sodium benzoate: sucralose:

Each treatment pack is composed of two bottles of 180 mL with about 176 mL of concentrate. The bowel cleansing preparation Eziclen®/Izinova® will be given orally on the evening of the day before colonoscopy. The total dose administered is 3/4 of the adult dose (product dispensed).

# Evening before the procedure (e.g.: 6:00 pm):

The two bottles of Eziclen®/Izinova® (180 mL X 2 concentrate sulphate salt solution) are to be diluted up to 1000 mL with water, using a 1000 mL graduated measuring glass. A total of 250 mL (1/4) of the preparation will be discarded. The remaining 750 mL of the preparation (3/4 adult dose) will be divided in two equal portions. The first portion of 375 mL will be drunk slowly in  $\frac{1}{2}$  to 1 hour, followed by an additional 750 mL of water over the next hour. The total ingested volume is 1125 mL.

# Approximately 2 hours after the start of drinking the first portion (e.g., 8:00 pm):

The second 375 mL portion of the Eziclen®/Izinova® preparation will be drunk slowly in ½ to 1 hour followed by additional 750 mL of water over the next hour. The total ingested volume is 1125 mL.

The total volume of preparation drunk is 750 mL, with an additional 1500 mL of water, for a total of 2250 mL. If a subject experiences difficulty in drinking the bowel cleansing preparation, a nasogastric tube will be placed, the rate of administration should not exceed 30 mL/kg/hour.

# 6.1.2 Klean-Prep®

The comparator, Klean-Prep® is a powder for oral solution packaged in 4 sachets.

Each sachet of Klean-Prep® contains the following active ingredients: 59.000 g macrogol 3350, 5.685 g anhydrous sodium sulphate, 1.685 g sodium bicarbonate, 1.465 g sodium chloride and 0.7425 g potassium chloride.

Each treatment pack is composed of 4 sachets with a total of 69 g of the product (powder for oral solution) included in each sachet.

Klean-Prep® (powder for oral solution) will be given orally on the evening of the day before colonoscopy. The complete dose of the preparation will be administered on the day prior colonoscopy, in the evening.

Evening before the procedure (e.g.: 6:00 pm):

PAGE 45/103

The 4 sachets are to be diluted. Each sachet is diluted in 1 litre of water. The dosage will be 70 mL/kg (which corresponds to the approved posology for that class of age and/or weight).

The volume to be taken will be calculated based on subject's weight and reported by study nurse or pharmacist on the subject's leaflet as a reference. The maximum volume administered will be 4000 mL.

The whole solution will be administered in two half doses (1 litre per hour), with a 1-hour pause between the two half doses.

Approximately 2 hours after the start of the drinking the first portion (e.g. 8:00 pm), the second portion of Klean-Prep® will be drunk.

If a subject experiences difficulty in drinking the bowel cleansing preparation a nasogastric tube will be placed, the rate of administration should not exceed 30 mL/kg/hour.

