# Evening before the procedure (e.g., 6:00 pm)

The 4 sachets are to be diluted. Each sachet is diluted in one litre of water.

The dosage will be 70 mL/kg (which corresponds to the approved posology for that class of age and/or weight). The maximum volume administered will be 4000 mL.

The whole solution will be administered in two half doses (1 litre per hour) with a 1-hour pause between the two half doses. If a subject experiences difficulty in drinking the bowel cleansing preparation, a nasogastric tube will be placed, the rate of administration should not exceed 30 mL/kg/hour.

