**PAGE 35/103** 

#### 4 SELECTION AND WITHDRAWAL OF SUBJECTS

#### 4.1 Inclusion Criteria

Subject MUST satisfy all of the following entry criteria before being allowed to participate in the study:

- (1) Provision of signed ICF to participate in the study obtained from the adolescent's parent(s)/ legal representative and a signed assent form from the adolescent according to local law
- (2) Male or female subjects between 12 to 17 years of age (inclusive)
- (3) Body weight more than 40 kg
- (4) Female of childbearing potential must have a negative pregnancy test
- (5) If female, and of child-bearing potential, subject must use an acceptable form of birth control (hormonal birth control, intrauterine device (IUD), double-barrier method, or depot contraceptive)
- (6) Routinely accepted indication for undergoing colonoscopy, including but not limited to polyposis coli diagnosis or surveillance, gastrointestinal bleeding, unexplained diarrhoea or constipation, surveillance of inflammatory bowel disease or confirmation of mucosal healing, abdominal pain, abnormal endosonography or manometry, anaemia of unknown aetiology, cancer surveillance
- (7) In the investigator's judgment, the parent(s)/legal representative are/is mentally competent to provide informed consent for the subject to participate in the study
- (8) In the investigator's judgement, subject is able and willing to follow study procedures including drug administration and response to questionnaires

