- Urine analysis by dipstick (pH, protein, ketones, bilirubin, blood, urobilinogen, nitrites, leukocytes, glucose and specific gravity, urine microscopic examination
- Blood and urinary samples for sulphate measurement
- Blood pregnancy test, if female of child-bearing potential. Urine pregnancy test will be performed only when blood tests including pregnancy have been performed prior to Visit 1.
- Indication(s) for colonoscopy to be collected
- Randomisation
- Drug accountability, study treatment dispensation by study nurse (with explanation of treatment administration)
- Subject/caregiver questionnaires dispensation by study nurse (with explanation of questionnaires including compliance measurement)
- Prior and concomitant medications including supplements, herbal medications and nonprescribed compounds
- Prior and concomitant non-drug therapies and surgical procedures
- Collection of AEs from the time of informed consent signature
- Subject status at the end of the visit

Records up to the time of premature termination should be completed. In the event that the subject was not receiving IMP, the primary reason will be recorded.

If any Visit 1 serum chemistry result is considered abnormal and clinically significant by the investigator result may be checked per investigator's decision. The abnormal significant result will be reported as an AE.

In case of non-inclusion of the subject, the primary reason will be recorded.

Following confirmation of eligibility for the study, subjects will be given a randomisation/treatment allocation number and allocated to one of the dosing groups specified in Section 6.1.

Caregivers and subjects will be provided with a subject leaflet containing instructions on how to administer the study preparation. Caregivers will be provided with a Treatment Acceptability Questionnaire (see Section 7.3.2.3) to report their child's experience with the study preparation, and a Symptom Scale to rate subject tolerability (see Section 8.6). Subjects/caregivers will complete these questionnaires during and after the treatment administration.

Subjects will be hospitalised for preparation. The treatment will be prepared by a nurse and administration will be monitored as described in Section 3.4. The nurse or caregiver will fill in

PAGE 42/103

the questionnaires or ensure that the subject fills in, as appropriate. If a subject is unable to complete the preparation, a nasogastric tube will be placed.

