# 7.3.2.2 Treatment/Compliance

The treatment questionnaire will be completed by the caregiver or subject after the subject completes each dose of preparation. The subject/caregiver will provide information about treatment preparation, residual volumes of preparation (volumes not taken by the subject) and start and stop times of intake. For the Eziclen®/Izinova® treatment only, information about the residual volume of water will be reported.

PAGE 48/103

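### Protocol 6.1.2 starts the second Klean-Prep portion at about 2 hours, 24 to 60 minutes earlier than its own volume, rate and pause imply

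*Protocol*

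**What the plan says.** Protocol 6.1.2 gives the Klean-Prep volume as 70 mL/kg and caps it: "The maximum volume administered will be 4000 mL". It then gives the split, the rate and the pause: "The whole solution will be administered in two half doses (1 litre per hour), with a 1-hour pause between the two half doses". The following paragraph gives a start time: "Approximately 2 hours after the start of the drinking the first portion (e.g. 8:00 pm), the second portion of Klean-Prep® will be drunk". The first portion is timed at 6:00 pm, also as an example.

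The synopsis, under the reference therapy, repeats the rate and pause ("The whole solution will be administered in two half doses (1 litre per hour) with a 1-hour pause between the two half doses") but has no 2-hour line for Klean-Prep. The SAP (3.2.1.2.10 and Appendix 1) gives only volumes, with at most 2000 mL per dose. Entry requires "Body weight more than 40 kg" (Protocol 4.1).

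The working instructions reach families and staff through a leaflet (Protocol 5.2.2): "Caregivers and subjects will be provided with a subject leaflet containing instructions on how to administer the study preparation". Its administration text is not in the documents.

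**The concern.** The rate, the pause and the start time are three statements about one schedule, and any two of them fix the third. For Klean-Prep they give different answers, so a site can follow two of them but not all three. Nothing else in the protocol or SAP says which sentence prevails.

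If centres follow different sentences, the end of intake moves in the Klean-Prep arm only, and by more in heavier subjects. That feeds into the time from last intake to the start of colonoscopy. The SAP added this endpoint (Table 2 and section 5) on the ground that it is a major contributor to preparation quality in adults. SAP 3.2.1.3.4 compares it between arms by ANOVA with a p-value. Weight class is also a planned subgroup (SAP 3.2.15).

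**Working it through.** **Inputs.** 70 mL/kg, 4000 mL maximum, two half doses, 1 litre per hour, 1-hour pause, second start at about 2 h (all Protocol 6.1.2); weight above 40 kg (Protocol 4.1); weight classes (SAP 3.2.15).

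**Formulas.** For weight w in kg:
- total volume V = min(70 × w, 4000) mL
- time to drink one half dose h = (V / 2) / 1000 hours
- second start implied by rate and pause = h + 1
- gap from the printed start = (h + 1) − 2 = h − 1
- pause left if the second portion starts at 2 h = 2 − h

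**Reproducing the printed 2 hours.** h + 1 = 2 needs h = 1, so a half dose of 1000 mL and a total of 2000 mL. That corresponds to 2000 / 70 = 28.6 kg, below the entry weight. The printed figure is therefore not reproduced exactly for any eligible subject.

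**Eligible weights.**

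| Weight | V (mL) | h (h) | Implied second start (h) | Gap (min) | Pause left with a 2 h start (min) |
|---|---|---|---|---|---|
| just above 40 kg | 2800 | 1.40 | 2.40 | 24 | 36 |
| 42.9 kg (3000/70) | 3000 | 1.50 | 2.50 | 30 | 30 |
| 50 kg | 3500 | 1.75 | 2.75 | 45 | 15 |
| 57.1 kg (4000/70) and above | 4000 | 2.00 | 3.00 | 60 | 0 |

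By SAP weight class the gap is 24 to 45 min (above 40 to 50 kg), 45 to 60 min (above 50 to 60 kg) and 60 min (above 60 kg).

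**End of intake, holding the printed 1 litre per hour.** Rate and pause give 2h + 1; a 2-hour start gives 2 + h. The difference is again h − 1: 3.80 v 3.40 h just above 40 kg (24 min), 4.50 v 3.75 h at 50 kg (45 min), and 5.00 v 4.00 h from 57.1 kg (60 min). This does not depend on the 6:00 pm example.

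**Keeping both the 2-hour start and the 1-hour pause.** The half dose would have to be drunk in 1 hour, which is 1.4 L/h just above 40 kg and 2.0 L/h from 57.1 kg, against the stated 1 L/h. Intake would then end at 3.0 h, which is 48 to 120 min before the 3.80 to 5.00 h given by rate and pause.

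**The 30 mL/kg/hour ceiling as the rate.** Up to 57.1 kg a half dose is 35 mL/kg, so it would take 35 / 30 h = 70 min and the second portion would start at 130 min, close to the printed time. But that ceiling stands in the nasogastric-tube sentence and does not replace the stated 1 litre per hour.

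**The case against.** The start time is qualified by *approximately* and the clock times are only examples, so asking for exact agreement demands a precision the protocol did not claim. This has force at the lightest weights, where 24 minutes may pass as approximate. It fails at the heavier ones: from 57.1 kg the printed start falls at the moment the first half dose ends, and the pause disappears.

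The consequences are also modest, and these points stand:
- Colonoscopy follows an overnight interval ("Colonoscopy will be performed on the morning following completion of the preparation"), of which the shift is a small part.
- The protocol collects "residual volumes of preparation (volumes not taken by the subject) and start and stop times of intake", and the endpoint uses actual times, so divergence between sites would be measured, not hidden.
- SAP 3.1.5 makes the secondary tests descriptive.
- Eziclen/Izinova timing is not rigid either: 6.1.1 allows half an hour to an hour for each portion.
- Dosing is in hospital and nurse-prepared, and the leaflet may already be consistent.

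The end-of-intake range of 24 to 60 min holds only while sites keep 1 litre per hour; the faster-drinking reading widens it, as shown above. Finally, this protocol version is dated 02 March 2020 with the study planned to end in Q2 2020, so on the plan's own dates corrected wording would reach few remaining subjects.

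None of this removes the contradiction within 6.1.2.

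**Conclusion.** The concern holds. The printed start of the second Klean-Prep portion is 24 to 60 minutes earlier than the volume, rate and pause in the same section imply. The gap exceeds 30 minutes above 42.9 kg and reaches its maximum at 57.1 kg. These figures rest only on numbers printed in the protocol.

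How many subjects fall in each range cannot be stated, because the weight distribution is not given. Whether sites in fact diverged depends on a leaflet that is not in the documents. No effect on the primary comparison is shown. The arithmetic is certain; the practical importance is minor to moderate. It should still be corrected, because this is the section that governs how the comparator is given.

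**What to change.** Reconcile the rate, pause and start-time sentences in Protocol 6.1.2, and check that the synopsis and the subject leaflet agree with the result. Which statement changes is for the sponsor's clinical team; this review does not choose between them. The synopsis does not contradict itself and needs editing only if the rate or pause is altered. The same 2-hour, 8:00 pm timing appears for Eziclen/Izinova in 6.1.1, where it fits the portion and water times, so the line may have been carried across. That is an inference, and it is worth checking.

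Optionally, use the intake start and stop times already collected for each dose (Protocol 5.1 and 7.3.2.2) and listed by subject (SAP 3.2.8) to describe the second-dose start and the pause actually followed in the Klean-Prep arm. Place this beside the analysis in SAP 3.2.1.3.4. If the wording can no longer change practice, this is the useful part.

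The cost is a few sentences, a check of the leaflet and, if the description is added, one short table. No new data are needed.

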#### 6.1.3 Rescue Treatment

A rescue treatment (normal saline enema, 1000 mL) may be administered only if clear discharge has not been obtained 1 hour prior to procedure. This rescue medication may be repeated until clear discharge is obtained. Sodium phosphate enemas are not to be used.

# 6.2 Prior and Concomitant Medication and Non-drug /Therapy

The use of concomitant medication will be recorded from 7 days prior to Visit 1 until completion of Visit 4 (Day 32(-5/+15), including sedation medications and intravenous fluids administered during colonoscopy.

No concomitant medication is forbidden. However, bowel cleansing will interfere with the absorption of medications. Concomitant oral medication administered within 1 to 3 hours of the start of the treatment and until the end of the cleansing process may be flushed from the gastrointestinal tract and the medication may not be absorbed properly. The therapeutic effect of regularly taken oral drugs with a narrow therapeutic index or short half-life (e.g. oral contraceptives, antiepileptic drugs, antidiabetics, antibiotics, levothyroxine, digoxin...) may be particularly affected.

Caution is advised in subjects with conditions, or who are using medications, inducing fluid or electrolyte disturbances, such as angiotensin converting enzyme inhibitors, calcium channel blockers, diuretics, lithium treatment, or other medications that might affect electrolyte levels. Caution is also advised when taking medicines known to prolong the QT interval.

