### Methodology:

- Multicentre, investigator-blinded, randomised Phase III comparative study
- In adolescents (male and female) >40 kg with routine indication for colonoscopy
- Eziclen®/Izinova® solution: oral administration at 3/4 adult dose versus Klean-Prep® (70 mL/kg, maximum 4000 mL), both administered as 1-day regimen on the evening before colonoscopy
- Subjects will be hospitalised from baseline (Visit 1, Day 1) to completion of colonoscopy (Visit 2, Day 2)
- The maximum duration of the study for each subject will be 47 days: Baseline (Visit 1) and treatment administration on Day 1, colonoscopy (Visit 2) on Day 2, phone contact (Visit 3) at Day  $4 \pm 1$ , 30-day follow-up at the final visit (Visit 4) on Day 32 (-5/+15, i.e. ranging from Day 27 to Day 47)

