### 4.2 Exclusion Criteria

If any of the following apply, the subject MUST NOT enter/continue in the study:

- (1) Subject with known or suspected ileus, gastrointestinal obstruction, gastric retention (gastroparesis), rectal impaction, toxic colitis, severe ulcerative colitis or toxic megacolon, advanced carcinoma, swallowing disorders
- (2) Subject with known or suspected inflammatory bowel disease (Crohn's disease, ulcerative colitis) in moderate to severe active phase defined by PCDAI >30 (Crohn's disease) or PUCAI >34 (ulcerative colitis)
- (3) Subject with bowel perforation or increased risk of bowel perforation, including connective tissue disorders or recent bowel surgery
- (4) Subject with previous significant gastrointestinal surgery (e.g. colostomy, colectomy, gastric bypass, stomach stapling)
- (5) Subject with uncontrolled pre-existing electrolyte abnormalities, or with electrolyte abnormalities based on Visit 1 laboratory results such as hypernatremia, hyponatremia, hyporahaemia, hypocalcaemia, uncorrected dehydration, or secondary to the use of medications such as diuretics or angiotensin converting enzyme (ACE) inhibitors judged clinically significant by the investigator
- (6) Subject with a prior history or current condition of severe renal (estimated glomerular filtration rate (eGFR) less than 30 mL/min/1.73 m2 as calculated by using the Schwartz bedside equation\* [13]), liver (ascites, Child-Pugh C), cardiac insufficiency (including congestive heart failure all grades) or hyperuricemia

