**PAGE 36/103** 

- \*The estimated GFR will be calculated in patients with elevated creatinine at baseline.
- (7) Female subject who is pregnant or lactating
- (8) Subject who has participated in another investigational drug treatment within the last 90 days before the first study visit
- (9) Subject with phenylketonuria
- (10) Subject with history of asthma or hypersensitivity to any ingredient of either drug product
- (11) Subject for whom intake of substances likely to affect gastrointestinal motility or urinary flow rate is required
- (12) Subject with requirement to take any other oral medication within 3 hours of starting the bowel preparation, as this may impact medication absorption
- (13) Subject with tendency for nausea and/or vomiting
- (14) Subject with impaired consciousness that predisposes them to pulmonary aspiration or who have known swallowing disorders
- (15) Subject with history of major medical/psychiatric conditions that, in the judgment of the investigator, would compromise safety in the study
- (16) Subject with mental or psychiatric condition rendering the subject unable to understand the nature, scope and possible consequences of the study, and/or evidence of an uncooperative attitude
- (17) Subject with a condition that, in the opinion of the investigator, might increase the risk to the subject or decrease the chance of obtaining satisfactory data needed to achieve the objectives of the study
- (18) Subject who has previous enrolment in this study or concomitant enrolment in other clinical studies

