#### 10.4.5 Efficacy Evaluation

As indicated in Section 7.1, the primary efficacy variable is the proportion of subjects with successful overall preparation evaluated with the scale (from 1 to 4) of the Cleansing Score as assessed by the colonoscopist.

A successful preparation will be defined as excellent (4) or good (3) preparation.

A failure preparation will be defined as:

- Fair (2) or poor (1) according to bowel cleansing
- Any subject who did not have a colonoscopy based on the investigator's assessment of the cleansing (insufficient faecal output, unclear faecal discharge, etc.) or due to preparation related AEs.
- Any subject for whom cleaning was not adequate for evaluation.
- Any subject for whom rescue treatment (saline enema) was needed.

The proportion of subjects with successful colon cleansing (graded as excellent or good) will be summarised along with the 95% confidence interval (CI) using the standard Wald asymptotic CI. The primary efficacy endpoint will be analysed using a logistics regression model including country as stratified variable, the interaction between country and treatment will be also investigated. The formal hypothesis test result (p-value) for treatment difference will be presented together with a two-sided 95% CI for the difference in success rates. The non-inferiority will be demonstrated if the lower limit of the 95% CI of that difference is higher than -15%.

If the non-inferiority is demonstrated, the superiority will be analysed based upon treatment difference. If the lower limit of the CI is greater than zero, Eziclen®/Izinova® is proven to be superior to the Klean-Prep®.

Secondary efficacy endpoints are presented in Section 7.2.

Results will be tabulated by treatment group and overall using descriptive summary statistics (mean SD, median, interquartiles and ranges) or frequency count with two-sided 95% CI when appropriate.

Time to clear effluent data will be analysed by using survival methods. The results will be presented both in summary tables (number of events, censors, median and interquartile time to event with 95% CI...) and graphically in Kaplan-Meier plots by treatment group and overall. This will be detailed in the SAP.

Other secondary endpoints will be analysed using Cochran-Mantel-Hænszel (CMH) chi-square for count (percentage) adjusting for country effect and two-way analysis of variance (ANOVA) for continuous parameters including treatment, country and their interaction as covariates.

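### Protocol 6.2 conflicts with the exclusion criteria on concomitant medication, and a good score reached with a non-study laxative is credited to the randomised preparation

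*Protocol*

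**What the plan says.** Protocol 6.2 states "No concomitant medication is forbidden". It then gives cautions about absorption and electrolytes. It also provides that "The use of concomitant medication will be recorded from 7 days prior to Visit 1 until completion of Visit 4".

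Protocol 4.2 opens with "If any of the following apply, the subject MUST NOT enter/continue in the study". Exclusion 11 is "Subject for whom intake of substances likely to affect gastrointestinal motility or urinary flow rate is required". Exclusion 12 begins "Subject with requirement to take any other oral medication within 3 hours of starting the bowel preparation". Section 6.1.3 (also 3.4 and the synopsis) rules out sodium phosphate enemas.

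The primary failure definition is in protocol 10.4.5, SAP 3.2.1.1 and SAP Appendix 1 item 3. It has four routes:
- a fair or poor score;
- no colonoscopy because of the cleansing or preparation-related adverse events;
- cleaning not adequate for evaluation;
- "Any subject for whom rescue treatment (saline enema) was needed".

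No other laxative or cleansing agent is mentioned. SAP 3.2.9 lists and tabulates concomitant medication but does not link it to the primary endpoint. SAP 2.1.2 removes from the per-protocol (PP) set only major deviations that affect the analyses, as defined in the Protocol Deviation Document.

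**The concern.** The two sections give sites different instructions. Section 4.2 bars subjects who require certain medicines; section 6.2 forbids none. Section 6.2 also treats oral medicines taken close to dosing, and diuretics, as matters for caution, although exclusions 11 and 12 bear on the same ground.

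The statistical consequence lies in the endpoint. The objective is to compare two oral preparations. By failing anyone who needs the enema, the plan already accepts that cleansing achieved with help is not a success of the preparation. It applies that principle to one agent only. Prior or as-needed laxative use is plausible, because the accepted indications include "gastrointestinal bleeding, unexplained diarrhoea or constipation" and section 6.2 sets no washout. An added agent that turns would-be failures into successes at a similar rate in both arms shrinks a true deficit. In a non-inferiority trial that is the anti-conservative direction. After randomisation, use could also differ by arm, because the staff who prepare and dispense treatment know the allocation.

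**Working it through.** **Plan's own figure.** Inputs from protocol 10.2: 85% success in each arm, margin 15 points, one-sided alpha 0.025, power 90%.

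n = [0.85×0.15 + 0.85×0.15] × (1.960 + 1.282)² / 0.15² = 0.255 × 10.507 / 0.0225 = 119.08. This gives the stated 120 per arm, and 120/0.96 = 125 randomised. Power at 120 per arm is 90.2%. The figure reproduces.

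**Sensitivity model.** The documents give no rate of laxative use and no effect of it, so r is assumed: the share of would-be failures turned into successes by a non-study agent. Success in an affected arm becomes p + r(1 − p). The starting truth is at the margin: 70% test, 85% comparator, 120 per arm.

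P(declare non-inferiority) = Φ[(d + 0.15)/SE − 1.96], where d is test minus comparator and SE = √[p_T(1 − p_T)/120 + p_C(1 − p_C)/120].

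With the same r in both arms, d = −15 × (1 − r) points. For r = 10%:
- p_T = 0.73, p_C = 0.865, d = −0.135;
- SE = √[(0.1971 + 0.1168)/120] = 0.0511;
- Φ(0.015/0.0511 − 1.96) = Φ(−1.667) = 4.8%.

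| Where the agent is used | r | Difference (points) | False non-inferiority |
|---|---|---|---|
| Nowhere | 0 | −15.0 | 2.5% |
| Both arms | 5% | −14.25 | 3.5% |
| Both arms | 10% | −13.5 | 4.8% |
| Both arms | 20% | −12.0 | 8.9% |
| Test arm only | 10% | −12.0 | 8.3% |
| Comparator arm only | 10% | −16.5 | 1.2% |

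Exact binomial enumeration of the Wald rule gives 2.6%, 3.6%, 5.1% and 9.5% for the first four rows. The normal approximation is adequate.

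**Cost in the reverse case.** If both preparations truly give 85% and r = 10% applies to the comparator only, p_C = 0.865 and d = −0.015. SE = √[(0.1275 + 0.1168)/120] = 0.0451. Power is Φ(0.135/0.0451 − 1.96) = 84.9%, against 90.2%.

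**Check on the remedy.** A failure rule drawn too widely dilutes the difference as well. If it turns a share g of successes into failures in both arms, d = −15 × (1 − g). At g = 10% the rates are 63.0% and 76.5%, SE = √[(0.2331 + 0.1798)/120] = 0.0587, and false non-inferiority is Φ(0.015/0.0587 − 1.96) = 4.4%. A rule that caught sedatives or antiemetics could therefore do about as much harm as the gap it closes.

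These calculations use the unadjusted Wald interval. The planned analysis adjusts for country.

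**The case against.** The strongest reply is that the opening is narrow and visible. Exclusion 11 plausibly removes subjects who need maintenance laxatives. Exclusion 12 limits other required oral drugs around dosing. Subjects are in hospital from Visit 1 to colonoscopy and take clear liquids only, and nurses prepare the treatment and monitor its administration. Medication is recorded. Nothing in the documents suggests that ward staff give extra laxatives. This stands, and it reduces the gap to non-required, as-needed or recent oral use. It does not supply a rule for that use when it appears in the data.

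Four stronger readings are tempting and are not supported:
- **That the saline enema is the only route to failure.** Three other routes exist. The point holds only among added cleansing agents.
- **That non-saline enemas escape.** Sodium phosphate enemas are banned. SAP Appendix 1 item 8 derives rescue from an eCRF question about any enema, and the dataset filter in SAP 3.2.1.2.7 selects on enema without naming saline. As collected, any enema is captured.
- **That the PP analysis must carry the same contamination because nothing is forbidden.** Protocol 12.1.2 makes breaches of the exclusion criteria violations. What leaves the PP set depends on the Protocol Deviation Document, which is not among the documents reviewed. The PP set is not an assured safeguard, but neither is it shown to fail.
- **That the bias always favours non-inferiority.** It reverses if use is concentrated in the comparator arm. Very large effects would need a large share of failures to be converted, for which the documents give no basis.

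**Conclusion.** The point holds in a limited form. Section 6.2 contradicts exclusions 11 and 12 and the enema ban in 6.1.3, and these must be reconciled. Separately, under the stated rule a score of 3 or 4 reached with a non-study oral laxative is a success in the primary mITT analysis.

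If such use converts a similar share of failures in both arms, or more in the test arm, it favours non-inferiority: 3.5% to 8.9% against 2.5% nominal for an assumed 5% to 20% in both arms. If it is concentrated in the comparator arm it works against the test product. Use before Visit 1 precedes randomisation and is balanced in expectation; use afterwards need not be. The direction therefore cannot be settled in advance. All sizes rest on an assumed conversion share and on a true difference at the margin, except the power figures, which assume equal 85% rates.

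**What to change.** 1. Reconcile protocol 6.2 with 4.2 (exclusions 11 and 12) and 6.1.3. Which medicines may be given is for the sponsor to decide.
2. Derive one flag from the concomitant-medication data: any non-study bowel-cleansing agent on a prespecified list, given between first intake and colonoscopy. Exclude sedation, analgesic and antiemetic drugs from the list, for the dilution reason shown above. The prior/concomitant codes in SAP 3.2.9 work by date, so the flag also needs a rule for missing times.
3. Count flagged subjects as failures in protocol 10.4.5, SAP 3.2.1.1 and Appendix 1 item 3, in line with the enema rule. At minimum, do so in a prespecified mITT sensitivity analysis.
4. State in the Protocol Deviation Document, before database lock, whether such use is a deviation that affects the PP set.

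The cost is some wording, a short drug list and one derived variable from data already collected. The observed success rate may fall slightly. Sample size does not change.
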